5.8.6. Management of Potential IMGN853 Infusion-related Reactions

Some patients treated with IV infusions of therapeutic antibodies have experienced concurrent infusion-related reactions with signs or symptoms that can be classified as acute allergic/hypersensitivity reactions (see NCI CTCAE, Version 4.03). The signs and symptoms may include headache, fever, facial flushing, pruritus, myalgia, nausea, chest tightness, dyspnea, vomiting, erythema, abdominal discomfort, diaphoresis, shivers, lightheadedness, hypotension, palpitations, and somnolence. Anaphylaxis might occur at any time during an infusion. Before any infusion is started, appropriate medical personnel, medication (e.g. epinephrine, inhaled beta agonists, antihistamines, and corticosteroids), and other required resources to treat anaphylaxis must be readily available. In general, Investigators should manage acute hypersensitivity reactions according to Institutional practices. General guidelines for management of acute reactions and subsequent retreatment with IMGN853 are provided in Table 6 below. Due to long half-life of the antibody, the potential exists for infusion—related reactions to recur after appropriate treatment; therefore, patients should be advised to seek immediate medical treatment if symptoms recur after discharge from clinic.

Patients who experience an infusion-related reaction during or immediately following administration of IMGN853 will have blood drawn for determination of drug concentration, antibodies to IMGN853 (HADA, HAHA). The sample should be obtained within three hours of the onset of the reaction and 1 week later. Such patients should undergo all scheduled efficacy and safety evaluations.

Table 6: Management Guidelines for Potential Infusion Reactions

Infusion Reaction CTCAE v4.03 Grade	Management	
Grade 1: Mild, transient reaction	 Maintain infusion rate unless progression of symptoms to ≥ Grade 2; if symptoms worsen, refer to guidelines below 	
	Promethazine (or equivalent) 150 mg PO prn nausea	
	Diphenhydramine (or equivalent) 25-50 mg PO or IV prn	
	Methylprednisolone 125 mg (or equivalent) IV prn	

ImmunoGen, Inc. Confidential Page 67 of 138

Infusion Reaction CTCAE v4.03 Grade	Management
Grade 2: Moderate	Interrupt infusion and disconnect infusion tubing from subject
	Promethazine (or equivalent) 150 mg PO prn nausea
	Diphenhydramine (or equivalent) 25-50 mg PO or IV prn
	Acetaminophen (or equivalent) 650 mg PO prn
	Methylprednisolone 125 mg (or equivalent) IV prn
	 After recovery from symptoms, resume the infusion at 50% of the previous rate and if no further symptoms appear, gradually increase rate until infusion is completed.
	 For subsequent dosing in future cycles, subjects should be pre-medicated with Dexamethasone 8 mg PO BID the day prior to IMGN853 administration and Acetaminophen 650 mg PO and Benadryl 25-50 mg PO 30-60 minutes prior to dosing.
Grade 3: Severe, prolonged	Stop infusion and disconnect infusion tubing from subject
reaction not rapidly responsive to symptomatic medication and/or	Administer Diphenhydramine (25-50 mg) IV
brief interruption of infusion; recurrence of symptoms following initial improvement; hospitalization indicated for	 Administer normal saline, epinephrine (0.2-0.5 mL of a 1:1000 dilution (0.2-0.5 mg)SQ or IM) and bronchodilators (nebulized albuterol, 2.5-5 mg in 3 mL of saline) as medically indicated
clinical sequelae	 Consider IV steroids (methylprednisolone (or equivalent) up to 0.5mg/kg Q 6h) to prevent recurrent or ongoing reactions
	Advise patient to seek emergency treatment and notify investigator/clinic if the infusion-related symptoms recur after discharge from clinic.
	• Report as a serious adverse event (see Section 9.1.1.2)
	 Investigators should confer with the sponsor regarding retreatment of the subject with IMGN853. If the investigator and sponsor agree that the subject could be rechallenged with IMGN853 then prophylaxis for an infusion-related reaction should occur in all subsequent cycles. For this, subjects should be pre-medicated with Dexamethasone 8 mg PO BID the day prior to IMGN853 administration and Acetaminophen 650 mg PO and Diphenhydramine 25-50 mg PO 30-60 minutes prior to dosing.

Infusion Reaction CTCAE v4.03 Grade	Management
Grade 4: Life-threatening consequences, urgent intervention indicated	 Immediately stop infusion and disconnect infusion tubing from subject Permanently discontinue study medication treatment Administer Diphenhydramine (or equivalent) 50 mg IV Administer normal saline, epinephrine (0.2-0.5 mL of a 1:1000 dilution (0.2-0.5 mg)SQ or IM) Administer bronchodilators (nebulized albuterol, 2.5-5 mg in 3 mL of saline) as medically indicated Administer IV steroids (methylprednisolone (or equivalent) up to 0.5mg/kg Q 6h) to prevent recurrent or ongoing reactions Report as a serious adverse event (see Section 9.1.1.2) Remove patient from study.

5.8.7. Monitoring and Management of Infusion-Associated Headaches

Infusion-associated headaches have been shown to be common in patients receiving IMGN853 under Schedule B. Patients should be advised of the risk of headache and should inform their treating physician if they develop an infusion-associated headache, to allow for appropriate evaluation and treatment. All patients dosed according to Schedule B should receive 325-650 mg of acetaminophen (PO or IV) approximately 30 minutes prior to each infusion of IMGN853.

5.8.8. Monitoring and Management of Treatment-emergent Eye Disorders

5.8.8.1. Monitoring - Potential Ocular Disorders

Changes in visual acuity, resulting from reversible keratopathy have been reported in other studies of DM4-containing immunoconjugates that use the SPDB linker (Younes 2012). Due to the observation of ocular disorders in patients treated with IMGN853 at the 5.0 and 7.0 mg/kg dose levels, (Section 1.9) ocular function is being carefully monitored. Complete ophthalmologic exams and ocular symptom assessments will be performed in all patients at baseline and post-treatment as described in the following schedule:

Table 7: Schedule for Ophthalmologic Assessments

Assessment	Screening	Day 1 (All Cycles)	Prior to Day 1 Dose (Every other Cycle) ⁴	End of Treatmen t	28-Day Follow Up
Ophthalmologic history – patients will be asked about ocular symptoms such as history of dry eye, and contact lens use	X				

ImmunoGen, Inc. Confidential Page 69 of 138

Assessment	Screening	Day 1 (All Cycles)	Prior to Day 1 Dose (Every other Cycle) ⁴	End of Treatmen t	28-Day Follow Up
Complete Exam ¹ : - Visual acuity (with/without corrective lenses; whichever best reflects the patient's usual functioning) - Slit lamp examination - Intraocular pressure measurement - Indirect fundoscopy	X^2		Patients who report treatment- emergent ocular AEs	X	X
Schirmer's test ⁴	X				
Ocular symptom assessment (blurred vision, ocular discomfort, etc.)	X	X		X	X
Prescribe 1% prednisolone (Cohort 5 Patients Only) ⁵	X				

¹ Performed by a board-certified ophthalmologist

If a subject develops ocular symptoms of any grade, the subject will be referred to an ophthalmologist for a complete examination. If a subject develops ≥ Grade 2 ocular symptoms, treatment with IMGN853 will be interrupted. In patients with clinical benefit, therapy may resume if ocular symptoms improve to Grade 1 or baseline within 21 days of the next scheduled IMGN853 dose. Subsequent examinations will be scheduled to occur in every other cycle going forward, from the time that the AE was initially reported, and at either the end of study or 28-day follow up visit. In the event of therapy being held for more than 14 days due to ocular symptoms, a subject showing clinical benefit prior to the onset of an ocular treatment-emergent adverse event may be allowed to resume therapy at a reduced dose after approval from the Sponsor.

5.8.8.2. Management Guidelines for Eye Disorders

Patients should also be firmly advised to avoid using contact lenses while on study. Baby shampoo and a soft cloth should be used to clean the eyes, and a warm compress at bedtime may be used to decrease any possible inflammation on the eyelid's surface. The use of UVA/UVB sunglasses is recommended for use outside in full daylight during the course of the study. If patients report signs or symptoms of ocular disorders, including, but not limited to, blurred

ImmunoGen, Inc. Confidential Page 70 of 138

² Within 14 days prior to Cycle 1, Day 1

³ Within 2 weeks prior to Day 1 Dose of every other cycle, required for patients who have experienced signs or symptoms of ocular toxicity and for those with blurred vision but normal eye exams.

⁴ For patients experiencing ocular symptoms, the Schirmer's test (with and without topical anaesthetic) will be repeated at the first ophthalmology exam and in subsequent ophthalmologic exams if clinically indicated.

⁵ Patients enrolled to Expansion Cohort 5 will receive primary prophylaxis with 1% prednisolone six times daily on Days 1-5 of each treatment cycle, followed by four times daily on Days 6-10 of each treatment cycle.

vision or eye irritation, the management and dose modification guidelines outlined in Table 8 should be followed.

Patients who have experienced study drug-related blurred vision symptoms, including those with including those with no obvious clinical findings on examination, will have a complete ophthalmic examination performed prior to the start of every other cycle and at the end of study or follow up visit following study discontinuation. Management of treatment emergent eye disorders with inflammatory characteristics should include corticosteroid eye drops and/or other measures as indicated by an ophthalmologist.

Table 8: Management of Ocular Disorders

Severity Grade (CTCAE v4.03 Grade)	Management	Guidelines for IMGN853 Dose Modifications
Grade 1	Complete eye exam as outlined in Table 7.Monitor for worsening symptoms	Continue IMGN853 dosing
Grade 2	 Complete eye exam as outlined in Table 7. Repeat complete exam as clinically indicated. Patients should have weekly symptomatic ocular assessments until the symptoms resolve to grade 1 or baseline (Section 5.9.1) or are deemed to be irreversible by the investigator 	 Hold IMGN853 dosing. Patients may be allowed to resume therapy at the same dose level unless there is a dosing delay > 14 days, in which case they should resume treatment at a reduced dose level (see Table 11)
Grade 3	 Complete eye exam as outlined in Table 7. Repeat complete exam as clinically indicated. Patients should have weekly symptomatic ocular assessments until the symptoms resolve to grade 1 or baseline (Section 5.9.1) or are deemed to be irreversible by the investigator. 	 Hold IMGN853 dosing. Patients may be allowed to resume therapy at a lower dose than the one they were receiving when their symptoms began (see Table 11).
Grade 4	 Complete eye exam as outlined in Table 7. Repeat complete exam as clinically indicated. Patients should have weekly symptomatic ocular assessments until the symptoms resolve to grade 1 or baseline (Section 5.9.1) or are deemed to be irreversible by the investigator. 	Permanently discontinue IMGN853 dosing.

5.8.9. Management of Non-Infectious Pneumonitis

Non-infectious pneumonitis has been observed following the administration of IMGN853 and may result in fatigue, shortness of breath, cough or respiratory distress. Drug-induced pneumonitis may be immediately life-threatening. If a patient presents with signs or symptoms consistent with pneumonitis and/or a clinically meaningful change in pulse oximetry value, the

ImmunoGen, Inc. Confidential Page 71 of 138

patient should be immediately evaluated according to institutional guidelines/practice. Patients are advised to notify their treating physician immediately if they experience new or worsening shortness of breath, cough or respiratory distress.

For patients diagnosed with pneumonitis without an infectious etiology, the management and IMGN853 treatment guidelines outlined in Table 9 should be followed.

Table 9: Management of Non-Infectious Pneumonitis

Severity Grade (CTCAE v4.03 Grade)	Medical Management of Pneumonitis	Guidelines for Dose Modifications
Grade 1	 Radiologic assessments (CT scan and/or chest x-ray) should be performed as clinically indicated. Monitor for pulmonary symptoms 	Continue dosing after discussion with the Sponsor.
Grade 2	 Radiologic assessments (CT scan and/or chest x-ray) should be performed as clinically indicated. Patient must be evaluated by a pulmonary specialist. Treatment with corticosteroids may be indicated as recommended by a pulmonary specialist and/or institutional guidelines. 	 Hold dosing until symptoms improve. IMGN853 may be resumed at same dose level after discussion with the Sponsor.
Grade 3	 Radiologic assessments (CT scan and/or chest x-ray) should be performed as clinically indicated. Patient must be evaluated by a pulmonary specialist. Treatment with corticosteroids until resolution of symptoms may be indicated as recommended by a pulmonary specialist and/or institutional guidelines. Bronchoscopy with lavage and/or biopsy when clinically feasible should be performed. The pneumonitis event must be followed until resolution 	 Hold IMGN853 dosing until symptoms resolve IMGN853 may be resumed at a lower dose level after discussion with the Sponsor.

ImmunoGen, Inc. Confidential Page 72 of 138

Severity Grade (CTCAE v4.03 Grade)	Medical Management of Pneumonitis	Guidelines for Dose Modifications
Grade 4	Radiologic assessments (CT scan and/or chest x-ray) should be performed as clinically indicated.	Permanently discontinue IMGN853 dosing.
	Patient must be evaluated by a pulmonary specialist.	
	Treatment with corticosteroids until resolution of symptoms may be indicated as recommended by a pulmonary specialist and/or institutional guidelines.	
	Bronchoscopy with lavage and/or biopsy when clinically feasible should be performed.	
	The pneumonitis event must be followed until resolution	

5.8.10. Monitoring and Management of Diarrhea

Mild to moderate diarrhea has been commonly reported in patients treated with IMGN853 (refer to IMGN853 Investigator's Brochure). Patients should be advised to contact their treating physician at the first sign of diarrhea. Patients may then be treated according to standard institutional practice. One suggested regimen would be the administration of 2 mg loperamide at the first sign of loose stool, with repeat dosing every 2 hours until symptoms resolve (Wadler 1998).

5.8.11. Monitoring and Management of Nausea and Vomiting

Nausea and vomiting have been reported in patients treated with IMGN853 in both dosing schedules. Patients should be advised to contact their treating physician at the first sign of vomiting or worsening nausea. Patients should be treated according to the ASCO Clinical Practice Guidelines for the use of antiemetics (Basch 2011) outlined in Table 10.

Table 10: Management of Nausea and Vomiting

Severity Grade (CTCAE v4.03 Grade)	Management
Grade 1	No premedication required as patients are already receiving 8 mg dexamethasone as part of their premedication for prevention of infusion reaction.
Grade 2	• Administer a 5- HT ₃ receptor antagonist on day 1 (e.g. palonosetron, granisetron, or ondansetron) in combination with dexamethasone on days 1-3 or treat as per institutional guidelines. Aprepitant may be added to the combination.
Grades 3 and 4	• Administer a neurokinin 1 receptor antagonist (e.g. aprepitant on days 1-3 or fosaprepitant on day 1), in combination with a 5- HT ₃ receptor antagonist on day 1 only, and dexamethasone on days 1-3 or 1-4 or treat as per institutional guidelines.

5.9. Treatment Guidelines

5.9.1. Re-treatment Criteria

5.9.1.1. To Begin a New Cycle of Treatment

In the absence of otherwise dose-limiting toxicity, for a patient to begin a new cycle of therapy, the following criteria must be met.

- ANC must be $\geq 1.5 \times 10^9 / L (1,500 / \mu L)$
- Platelet count must be $\geq 75 \times 10^9/L (75,000/\mu L)$
- All non-hematologic toxicities for which a causal association to study treatment cannot be ruled out, must be ≤ Grade 2 (except alopecia) or returned to baseline; the exception to this rule is treatment-emergent ocular symptoms, which must have recovered to < Grade 1 or baseline

If the patient does not meet these criteria, dosing will be delayed and the patient should be reevaluated within 48-72 hours. Dosing may resume if these criteria have been met. However, if the next cycle is delayed by greater than 14 days because of insufficient recovery from a treatment-related toxicity, this will be viewed as a dose-limiting event (Section 4.1.4). For patients treated on either dosing schedule, if the next cycle is delayed due to treatment-related toxicity by greater than 21 days then the patient should be removed from study treatment. In such cases, continuation of study treatment may be considered for those patients who have experienced clinical benefit if agreed upon between the Sponsor and the Investigator.

The use of granulocyte growth factors in accordance with ASCO guidelines may be implemented at the discretion of the treating physician after Cycle 1.

ImmunoGen, Inc. Confidential Page 74 of 138

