4.1.4. Definition of Dose-Limiting Toxicity (DLT)

Dose limiting toxicity (DLT) will be defined as a TEAE or abnormal laboratory value related to study treatment (i.e., assessed as unrelated to disease, intercurrent illness, or concomitant medications), including those TEAEs and abnormal laboratory values that result in a failure to

ImmunoGen, Inc. Confidential Page 59 of 138

meet the criteria for re-treatment. DLTs will be considered related to the investigational agent unless there is clear evidence of an alternative explanation and this attribution is agreed to by the CRC.

For the purposes of dose escalation and determination of the MTD, only DLTs that occur during the first cycle will be necessarily considered for decisions regarding dose escalation. Clinically significant toxicities or treatment-emergent adverse events that meet the definition of dose limiting but occurring after Cycle 1 (dose modifying events) may be considered when determining the RP2D.

If a patient experiences a DLT as outlined in Table 5, the study treatment must be stopped and the toxicity (ies) in question must be followed until resolution or stabilization. If treatment is to be resumed then retreatment criteria must be met (Section 5.9.3) and administration must be resumed at a lower dose (Section 4.1.3).

Table 5: DLT Definitions

TOXICITY	DLT DEFINITION CRITERIA			
Dose delays	Failure to meet re-treatment criteria within the specified timeframe			
Hematology	CTCAE Grade 4 neutropenia ≥ 7 days.			
	• CTCAE Grade 3 or 4 neutropenia with single temperature reading ≥ 38.3°C or sustained temperature reading of > 38°C for > 1 hour			
	CTCAE Grade 3 thrombocytopenia, associated with clinically- significant bleeding that requires transfusion therapy			
	CTCAE Grade 4 thrombocytopenia			
Non-hematologic and other DLTs	• ≥ CTCAE Grade 3 nausea or vomiting despite the use of optimal anti- emetic treatments			
	• ≥ CTCAE Grade 3 diarrhea despite the use of optimal anti-diarrheal treatments			
	• Other non-hematologic toxicities of CTCAE ≥ Grade 3 except for the following:			
	AEs related to underlying disease			
	o Alopecia			
	 CTCAE Grade 3 fatigue 			
	 Lymphopenia is not considered DLT unless accompanied by clinically-significant infection 			
	 Isolated, asymptomatic Grade 3 abnormalities in biochemistry laboratory values that last for ≤ 7 days. This includes electrolyte abnormalities that respond to medical intervention. 			

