5.9.4. Dose Modification Guidelines

5.9.4.1. Dose Reduction Following DLT

Patients who develop DLTs or adverse events requiring holding of the study drug may resume treatment at a reduced dose level as shown in Table 11 provided the criteria outlined in Section 5.9.4.2 are met.

Table 11: Dose Modification Guidelines

Dosing Schedule	If the patient was receiving IMGN853 at:	Dose should be reduced to:	
Schedule A	6.0 mg/kg	5.0 mg/kg	
	5.0 mg/kg	4.0 mg/kg	
Schedule B*	2.0 mg/kg	1.8 mg/kg	
	1.8 mg/kg	1.1 mg/kg	

^{*}IMGN853 should be dose-reduced one dose level; a second dose reduction may be allowed as needed. Dose reductions to intermediate dose levels may be allowed based on emerging data with the approval of the Sponsor.

Amendment 10 Update: Schedule B will not be evaluated further in the current study.

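### For Grade 2 pneumonitis, Sections 5.9.1.1, 5.9.3, 4.1.4 and Table 9 do not agree on re-treatment, on the dose after a hold over 14 days, or on whether that hold is a DLT.

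*Protocol*

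**What the plan says.** **New-cycle criteria.** Under 5.9.1.1, non-hematologic toxicities possibly caused by study treatment "must be ≤ Grade 2 (except alopecia) or returned to baseline", and "the exception to this rule is treatment-emergent ocular symptoms". A patient who fails is delayed and re-evaluated, and "Dosing may resume if these criteria have been met". If the next cycle slips by more than 14 days "because of insufficient recovery from a treatment-related toxicity, this will be viewed as a dose-limiting event", with a reference to 4.1.4. Beyond 21 days the patient should leave study treatment, unless there is clinical benefit and the sponsor and investigator agree to continue.

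**Pneumonitis guidance.** Table 9 in 5.8.9, added in Amendment 10, says for Grade 2: "Hold dosing until symptoms improve", and then "IMGN853 may be resumed at same dose level after discussion with the Sponsor". It gives no target grade and no limit on the hold. Table 8, for Grade 2 ocular events, allows the same dose only if the delay is not more than 14 days.

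**Criteria cited in the visit schedule.** Sections 10.3.1, 10.4.1 and 10.6.1 and Appendix A cite 5.9.3 for re-treatment from Cycle 2 onward. Section 5.9.3 is titled for use after a DLT. It sets Grade 1 or lower, or baseline, for clinically significant toxicities, and says a delay over 14 days *may* (not *will*) be treated as dose-limiting.

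**After a DLT.** Section 4.1.4 says "administration must be resumed at a lower dose (Section 4.1.3"; 5.9.4.1 says patients "may resume treatment at a reduced dose level as shown in Table 11".

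**DLT definition.** Table 5 counts failure to meet the re-treatment criteria in time as a DLT. SAP 6.3 repeats the 4.1.4 definition without adding to it.

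**The concern.** One patient state, ongoing treatment-related Grade 2 pneumonitis on Day 1 of a cycle, is covered by three sets of criteria with different thresholds, and by two rules for the dose after a long hold. None of them refers to Table 9 or says which takes precedence. Section 5.8.9 warns that drug-induced pneumonitis can threaten life at once, and SAP 6.2 lists pneumonitis among the events of special interest, so this is a poor place for an unstated hierarchy.

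The statistical stake is the DLT count. Whether a long hold is recorded as a DLT depends on which section the site or the Cohort Review Committee (CRC) reads. That count feeds the 33% expansion rule in 4.1.5 and 11.1 when the event arises in Cycle 1. Events after Cycle 1 may be weighed in choosing the RP2D, a primary endpoint.

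**Working it through.** The plan gives no figure to reproduce. The check follows one case through the text: a patient in an expansion cohort at 6.0 mg/kg every three weeks, with treatment-related Grade 2 pneumonitis still present on Day 1 of Cycle 2. I assume adequate blood counts, a lower grade at baseline, and a clinically significant event.

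**Step 1. May the cycle begin?**

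| Source | Test | Result |
|---|---|---|
| 5.9.1.1 | Grade 2 ≤ Grade 2; not ocular | Toxicity criterion met |
| Table 9 | Grade 2 | Hold |
| 5.9.3, cited by the visit schedule | Grade 2 > Grade 1 | Criterion not met |

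**Step 2. Which dose on resumption?**

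| Length of hold | Table 9, Grade 2 | General rules |
|---|---|---|
| 14 days or less | Same dose allowed after sponsor discussion | 14-day rule not triggered; no disagreement on dose |
| More than 14, up to 21 days | Same dose still allowed | 5.9.1.1: dose-limiting, so 4.1.4 requires a lower dose; 5.9.3: dose-limiting at discretion |
| More than 21 days | Silent | 5.9.1.1, 5.9.3 and 5.9.5: off treatment, unless clinical benefit and agreement |

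For this patient the first Table 11 reduction is from 6.0 to 5.0 mg/kg. The same-dose and lower-dose readings therefore differ by 1.0/6.0 = 16.7% of the current dose.

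**Step 3. Is a hold over 14 days a DLT?** Grade 2 pneumonitis is not a DLT by severity, because the Table 5 row for other non-hematologic toxicities starts at Grade 3. The only route is the delay.

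- Table 5 delay row, read with 5.9.1.1: the patient did not fail the re-treatment criteria, so it is not triggered.
- Table 5 delay row, read with 5.9.3: the patient failed them, so it can be triggered.
- 14-day sentence in 5.9.1.1: dose-limiting.
- 14-day sentence in 5.9.3: may be dose-limiting.

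**Step 4. Effect on the expansion rule.** Enrollment to a cohort stops if at least 33% of its treated patients have a Cycle 1 DLT. I assume that a late start of Cycle 2 caused by a Cycle 1 toxicity is attributed to Cycle 1.

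- Cohorts of 20 (2, 3 and 4): one patient is 1/20 = 5 percentage points.
- Cohorts of 40 (1 and 5): one patient is 1/40 = 2.5 percentage points.
- In a full cohort, one reclassified patient changes the outcome only at the margin: 6/20 = 30% against 7/20 = 35%, or 13/40 = 32.5% against 14/40 = 35%. The rule applies at any time, so one patient weighs more while a cohort is small.

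**The case against.** The strongest reply is that Step 1 is not a contradiction. The 5.9.1.1 criteria are conditions that must be satisfied before dosing; meeting them permits dosing and does not oblige it. Table 9 is later and more specific, and 5.8.9 says it should be followed for diagnosed non-infectious pneumonitis. A site that holds at Grade 2 complies with both, and 5.9.3 points the same way. This stands. A reader might infer that two sites following the protocol could treat the same patient in opposite ways, but that would require one of them to disregard Table 9. What remains is that no precedence is stated, and that naming ocular symptoms as the exception suggests there is no other.

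On Step 2, the same-dose wording in Table 9 is permissive and the lower-dose wording in 4.1.4 is mandatory, so resuming at a lower dose satisfies both. It is also tempting to say that a pneumonitis hold has no time limit. That is true only of the Table 9 cell, because the general 14-day and 21-day rules cover any treatment-related toxicity. What stands is that Table 9 lacks the 14-day qualifier found in Table 8, and that the mandatory route depends on 5.9.1.1 being read in preference to 5.9.3.

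A reader might also see a second dose conflict: 4.1.4 points to Section 4.1.3, where Table 3 has 3.3 mg/kg below 5.0, while Table 11 has 4.0. The documents do not support this. Table 3 lists planned escalation levels and does not contain 6.0 mg/kg, the dose in use, so it cannot serve as the reduction ladder. Sections 5.9.3 and 5.9.4.1 and Table 8 all lead to Table 11. The 4.1.4 pointer is out of date and no more.

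**Conclusion.** The inconsistency is real but limited; it should be fixed. For treatment-related Grade 2 pneumonitis, the re-treatment threshold is Grade 2 in 5.9.1.1, Grade 1 in 5.9.3 for clinically significant toxicities, and a hold until symptoms improve in Table 9. After a hold over 14 days, the dose on resumption and the DLT status depend on the section read. Holds of 14 days or less raise no disagreement about dose.

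The effect on the expansion rule is 5 percentage points per patient in a 20-patient cohort and 2.5 in a 40-patient cohort, and only for events arising in Cycle 1, on the attribution assumption in Step 4. Later events enter only through the RP2D judgement. The documents do not say how often Grade 2 pneumonitis leads to a hold over 14 days, so the number of patients affected cannot be stated. This review takes no position on which rule is clinically right.

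**What to change.** Reconcile the following, with the sponsor deciding the content:

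1. Sections 5.9.1.1 and 5.9.3 and Table 9, with a statement of which governs Grade 2 pneumonitis at the start of a cycle.
2. Table 9 Grade 2 with the 14-day and 21-day rules in 5.9.1.1, 5.9.3 and 5.9.5, and with the dose rule in 4.1.4. The same classification of a delay over 14 days should appear in 5.9.1.1 and 5.9.3.
3. Section 4.1.4 and Table 5, stating whether a Table 9 hold over 14 days is a DLT and to which cycle it is attributed. Carry this into SAP 6.3 so that the DLT listing follows one rule.
4. The re-treatment references in 10.3.1, 10.4.1, 10.6.1 and Appendix A, so that they cite the intended criteria.
5. As a minor point, the 4.1.4 pointer to Section 4.1.3, with the dose-modification table in 5.9.4.1.

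The cost is wording in a protocol clarification or amendment and a line in the SAP. No procedures, visits or patients are added.
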